### Design Overview

A pilot study will be conducted with 40 PLWH over 3 months. Participants will be randomly assigned to CHAMPS Pilot (intervention) or a standard-of-care control arm.

**Intervention Arm:** The CHAMPS Pilot intervention, outlined in Table 1, is a 3-month intervention guided by BA2C. The CHW will be demographically-matched to our study participant.

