### Randomization

Using the randomization approach described below, there will be random or minimally biased assignment of subjects to study arms. Randomization will be achieved through a blocked design utilizing permuted blocks of random sizes. The design ensures equal representation of treatment assignment across groups and protects the study team and investigators from easily anticipating treatment allocation. Randomization to CHAMPS Pilot or standard of care is 1:1. Participants will be randomized using computer-generated random numbers at baseline. The randomization database will be stored on a password protected computer at Columbia University and will only be accessible to PI [name]. Following completion of the informed consent and baseline assessment, participants will be randomly assigned to one of two trial arms in REDCap.

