**Table 4. Measures and Schedule of Events**

	Screening	Baseline	3 mos
Sociodemographic:(e.g., age, race/ethnicity, education, housing)		X	
Primary Outcome Measures			
Viral Load through dried blood spot kit	X		X
Secondary Outcome Measures			
ART adherence (SRSI)  and the CleverCap (intervention group only)	X		X
Additional Outcome Measures			
Quality of Life (PROMIS-29) 		X	X
HIV Symptom Index 		X	X
Engagement in HIV Care 		X	X
Mediators			
The HIV Medication Taking Self-Efficacy Scale		X	X
Motivation and outcome expectancies of ART adherence are assessed as three separate dimensions: attitudes, norms, and behavioral intentions to adhere to ART medication 		X	X
Self-regulation skills, which include self-monitoring, goal-setting, and enlistment of self-incentives/plans 		X	X
HIV-regulated Stigma 		X	X
Moderators			
Alcohol, Smoking & Substance Involvement Screening Test (ASSIST) 		X	X
Depression and Anxiety (Beck Symptom Inventory) 		X	X

and has ceiling effects. Finally, the electronic pill box is limited to data collected from the intervention group. While this is a limitation, providing the electronic pillbox to the standard of care (control group) is likely to bias our intervention effects since this pillbox will, in fact, have intervention effects as we have found from our preliminary findings from our WiseApp trial. We closely considered each of these limitations and have, therefore, decided that this three-pronged (i.e., viral load, self-report, and electronic pillbox) approach which will provide the most rigorous approach to measuring our primary and secondary outcomes of viral suppression and ART adherence.

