## **Data Analysis**

The distribution of all variables will be assessed, as will the correlations between all variables and the primary/secondary outcomes. We will assess for patterns of missing data, which are expected to be low as the study utilizes computer-assisted self-interview (CASI) for sensitive data, which reduces participant nonresponse. The primary anticipated reason for missing data is attrition due to loss to follow-up. Based on our preliminary studies, we are accounting for 20% attrition from randomization to the 3-month assessment.

All multivariate analyses will be preceded by standard descriptive bivariate analyses to describe key variables and relationships among them. These analyses will include means, frequency tables, histograms, and examination of distributions. All statistical tests will be two-sided tests with the level of significance at 0.05. The primary hypothesis 1 will be a comparison of viral suppression (primary outcome) between CHAMPS Pilot and standard of care. We will also compare the drop in viral load (measured in logarithmic scale with base 10) between the two groups. Our secondary and related outcome is ART adherence measured in two ways: 1) a single-item self-report measure, an empirically validated instrument (SRSI) and 2) electronic pill bottle data which we will be collecting in the intervention group since all participants will receive a CleverCap bottle for their medications. All the analyses will be based on initial assignment to groups, using the intention-to-treat principle.

The primary hypothesis 1 ( $H_1$ ) will be tested using a generalized linear mixed model (GLMM) with logit-link function for binary outcomes (i.e., viral suppression) or a linear mixed model (LMM) for continuous outcomes (i.e., viral load measured in logarithmic scale) to account for the non-independence of repeated measurements within individuals. The models will include a random intercept and fixed effects for intervention group, time, and interaction term of group and time which is for testing efficacy of the intervention. The model may include

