stratification variables, age, and sex as covariates. A site by group interaction will be also examined and included in each model (above) if significant at the .05 level. All analyses will be tested for goodness-of-fit using the Wald-type test, which shows satisfactory performance for models with fewer (<5) covariates. A similar GLMM will be used to test sustainability of the intervention at month 3. For this analysis, we will conduct a non-inferiority test to compare viral suppression rate between month 3 and baseline. For primary hypothesis 2 ( $H_2$ ), testing for intervention effect on ART adherence measured by SRSI (secondary outcome), we will use a similar LMM as mentioned above. For electronic pill bottle data in the intervention group, we will also examine the trend of electronic pill bottom data over time with a GLMM which will include a first-order autoregressive (AR1) covariance structure, as described by Hedeker and Gibbons. We will also aggregate the electronic pill bottle data at different time points (0 and 3 months) and examine the association between the electronic pill bottle data and ART adherence data measured by SRSI using Spearman nonparametric correlation. Similar GLMMs or LMMs will be used for secondary outcomes, with GLMMs for binary outcomes and LMMs for continuous outcomes.

Aim 2. Conduct follow-up interviews to assess the barriers and facilitators to the recruitment, enrollment and retention procedures and to understand the acceptability of the intervention.

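### The SRSI test compares change scores between arms; adjusting month-3 SRSI for the entry value would use the same data more efficiently

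*Combined protocol and SAP*

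**What the plan says.** The Data Analysis section under Aim 1 gives one model form for the between-arm tests: a random intercept, with fixed effects for group, time and their interaction. The interaction is the efficacy test. For SRSI it states "testing for intervention effect on ART adherence measured by SRSI (secondary outcome), we will use a similar LMM as mentioned above". The covariates that may be added are stratification variables, age and sex; the entry value of the outcome is not among them. The other outcomes are covered by "Similar GLMMs or LMMs will be used for secondary outcomes, with GLMMs for binary outcomes and LMMs for continuous outcomes", the only sentence that could apply to the continuous questionnaires.

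Table 4 schedules SRSI twice, at screening and at 3 months. Randomization follows consent and the baseline assessment, so entry SRSI precedes allocation and is a legitimate covariate. The limitations text around Table 4 says that the self-report measure is biased and "has ceiling effects. Finally, the electronic pill box is limited to data collected from the intervention group". SRSI is therefore the only adherence measure available in both arms.

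**The concern.** With two visits, a group-by-time interaction subtracts the entry value instead of adjusting for it. Subtraction is the efficient choice only when entry and follow-up are almost perfectly correlated; otherwise the change score carries extra noise. A ceiling aggravates this, because participants who enter near the top have little room to improve.

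At stake is precision. Sample Size and Power Calculation makes effect-size estimation for later trials a purpose of the study, so a noisier estimate from about 32 people is a weaker planning input even though no power is claimed. The point concerns SRSI and the continuous questionnaires, not the logistic model for viral suppression.

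**Working it through.** **Inputs from the plan.** "A pilot study will be conducted with 40 PLWH over 3 months" and "Randomization to CHAMPS Pilot or standard of care is 1:1" give 20 per arm. "we are accounting for 20% attrition from randomization to the 3-month assessment" leaves 40 × 0.8 = 32, or 16 per arm if losses are even. "All statistical tests will be two-sided tests with the level of significance at 0.05".

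**Inputs not in the plan (assumed).** Six SRSI response levels; entry to month-3 correlation rho; share in the top category at entry; effect size in SD units. The plan states no SRSI power, so there is no figure to reproduce.

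**Step 1: what the planned test is.** With complete data the random intercept cancels in each person's change, and the interaction estimate is the mean change in CHAMPS minus the mean change in control. With equal SDs at both visits, the per-person variance is:
- change: 2(1 − rho)SD²
- month 3 adjusted for entry: (1 − rho²)SD²
- ratio, adjusted to change: (1 − rho²) / [2(1 − rho)] = (1 + rho)/2

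| rho | ratio | effective sample (1/ratio) | CI narrower by (1 − √ratio) |
|---|---|---|---|
| 0.3 | 0.65 | +54% | 19% |
| 0.5 | 0.75 | +33% | 13% |
| 0.7 | 0.85 | +18% | 8% |

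This step needs no effect size.

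**Step 2: power without a ceiling.** Power ≈ Φ(δ / [s√(2/16)] − 1.96), where s is the square root of the variance above. At rho 0.5 and δ = 0.8 SD, change has s = 1.000, so 0.8/0.3536 = 2.263 and Φ(0.303) = 62%. Adjusted has s = 0.866, so 2.613 and Φ(0.653) = 74%. Likewise:
- rho 0.3, 0.8 SD: 48% against 66%
- rho 0.5, 0.5 SD: 29% against 37%
- rho 0.7, 0.8 SD: 83% against 89%

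**Step 3: power with a ceiling.** Latent bivariate normal values were cut into six categories, with 16 per arm and 1,000 simulated trials per row (Monte Carlo standard error at most 1.6 points). A shift of 0.3 SD common to both arms was included, except in the 5% rows. Entries are the percentage of trials rejecting.

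| rho | effect | ceiling | change test | linear ANCOVA | rank ANCOVA | proportional odds |
|---|---|---|---|---|---|---|
| 0.5 | 0 | 25% | 3.8 | 3.5 | 3.1 | 4.4 |
| 0.5 | 0.5 SD | 25% | 19.8 | 28.4 | 27.1 | 32.7 |
| 0.7 | 0.5 SD | 10% | 32.5 | 36.9 | 36.3 | 41.6 |
| 0.5 | 0.8 SD | 5% | 50.2 | 61.3 | 61.5 | 66.7 |
| 0.5 | 0.8 SD | 25% | 35.2 | 52.9 | 55.1 | 60.2 |
| 0.7 | 0.8 SD | 5% | 68.3 | 76.0 | 76.1 | 79.2 |
| 0.7 | 0.8 SD | 10% | 63.1 | 73.6 | 76.0 | 79.2 |
| 0.7 | 0.8 SD | 25% | 47.1 | 64.9 | 65.6 | 70.8 |

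Gain over the change test, across the three adjusted methods:
- 0.5 SD: from 36.3 − 32.5 = 3.8 points to 32.7 − 19.8 = 12.9.
- 0.8 SD: from 76.0 − 68.3 = 7.7 points to 60.2 − 35.2 = 25.0. A separate simulation with the same sample size and category count found gains as low as 5.

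At rho 0.5 and 0.8 SD with 40% at the ceiling (4,000 runs), change had 25%, linear ANCOVA 46% and rank ANCOVA 48%. As the assumed ceiling goes from 5% to 25% to 40%, the linear ANCOVA advantage goes from 11 to 18 to 21 points. Both methods lose power; the change score loses more.

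**Step 4: where the gain comes from.** Linear ANCOVA is also a Gaussian method. Relative to it, rank ANCOVA adds about −1 to +3 points and proportional odds about 3 to 7.

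**Step 5: the fitted model.** A REML mixed model using all 40 entry values with 20% dropout gave 42% at rho 0.5, 0.8 SD and 25% ceiling (250 runs, standard error √(0.42 × 0.58/250) = 3 points, Wald z test). Against that, linear ANCOVA at 53% gains about 11 points, inside the range above.

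**The case against.** The strongest defence is that nothing here is invalid. A group-by-time mixed model is standard, its type I error is close to nominal, and it uses entry data from everyone randomized, which fits the intention-to-treat statement. The study is a 40-person feasibility pilot with no power claim, and SRSI is labelled a secondary outcome. The ceiling is disclosed, distributions will be examined, and goodness of fit will be tested.

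Most of that stands, and it makes this an efficiency point. Two parts do not settle it. No fallback is named if the fit is poor. Keeping dropouts' entry data does not require the planned interaction test: a mixed model with a common baseline mean keeps them too.

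A reader might infer more than the documents support:
- **That the Gaussian model is the fault and an ordinal or rank method the cure.** Step 4 shows otherwise. Nor does adjustment remove the ceiling, since month 3 is capped as well.
- **That the trial would gain a fixed amount, say 20 points.** That needs an effect near 0.8 SD with a moderate correlation and ceiling, none of which is stated. The main eligibility section admits people by unsuppressed viral load, by self-report or by a missed visit, so the share at the top on entry is unknown.
- **That the plan itself concedes SRSI is ordinal by "using Spearman nonparametric correlation".** That method is for the association of SRSI with pill-bottle data, where skew in either variable would justify it.
- **That the steps of the scale are unequal.** The response scale is not described.
- **That the change has no downside.** A plain month-3 ANCOVA drops the 8 or so participants expected without follow-up (20% of 40).

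**Conclusion.** The concern holds as a matter of efficiency. The planned SRSI test is valid but, for complete data, is a change-score comparison that leaves precision unused, and the acknowledged ceiling widens the gap. For continuous scales the variance ratio (1 + rho)/2 assumes only equal SDs at the two visits. For SRSI the gain of roughly 4-13 points at 0.5 SD and 5-25 points at 0.8 SD rests on 16 evaluable per arm, six response levels, and assumed correlations and ceiling shares. The direction was the same in every non-null scenario tried; the size cannot be fixed from the documents. Importance is moderate: SRSI is secondary in this pilot, but it carries the hypothesis that the plan numbers as its second primary one.

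**What to change.** In Data Analysis under Aim 1, replace the SRSI model sentence with a month-3 comparison adjusted for entry SRSI. Use either linear ANCOVA or, to keep dropouts' entry data, a mixed model for both visits with a common baseline mean in the two arms. Report the adjusted difference with a 95% CI. Name a baseline-adjusted proportional-odds model or rank ANCOVA as a sensitivity analysis for the ceiling. Analyse the continuous questionnaires the same way, each adjusted for its own baseline score. If a power gain is quoted, give it as a range with its assumptions.

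The cost is a wording change; every value needed is already scheduled in Table 4. The downsides are small: the ordinal or rank sensitivity analysis has a less familiar effect measure and may meet sparse categories with about 32 people, and plain ANCOVA omits those without month-3 data.

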## Data Analysis

### Qualitative Data Analysis of Interview Data

The study team will meet and review transcripts and notes from the interviews. [name] has extensive experience in qualitative analysis and will work with two research assistants to code the transcripts. Field notes and transcripts will be analyzed by the researchers using NVivo™ (QSR International, Victoria, Australia) software. Participants' statements will be captured using memoing and then sorted into the categories of interest. Open coding will be used to develop initial data categories. Some codes will be derived from the questions included in the interview and other codes will emerge from themes and patterns identified in the narratives. An initial set of codes will be independently generated by two coders. Codes will then be compared and synthesized to result in shared coding categories and sub-categories, all with definitions, inclusion and exclusion criteria, and examples. Coders will discuss discrepancies until they reach consensus. Findings will guide modifications of *CHAMPS Pilot*, if warranted.

Scientific Rigor: The team will adhere to qualitative research processes to ensure the credibility, confirmability, dependability, and transferability of the qualitative data from these analyses. To support the credibility of the data, we will conduct peer debriefing. We will also use "member checks," i.e., sharing of initial data interpretations with participants to ensure accurate interpretations. Triangulation of findings, along with reflexivity, will enhance the confirmability of the interpretations. The investigators will carefully record an audit trail and keep extensive field notes to facilitate transferability of study findings into other contexts.

## RISKS, BENEFITS & MONITORING

### Risks to Human Subjects

#### Research Environment and Commitment to Protection of Human Subjects:

Columbia University Irving Medical Center (CUIMC) is committed to safeguarding the rights and welfare of human subjects in all research activities, and has a current Assurance of Compliance with the Office for Human Research Protections (OHRP). The investigators will follow all required policies related to the protection of human subjects. All investigators have fulfilled human subjects protection and Health Insurance Portability and Accountability Act (HIPAA) training requirements (including CITI basic and refresher courses, Good Clinical Practices, and conflicts of interest) and are up-to-date with these certifications. The study described in this application will be reviewed and approved by the Columbia University Institutional Review Board. All prospective participants will be fully informed of the intent of the study and expectations of participants prior to enrollment using an IRB-approved informed consent form.

### Human Subjects Involvement, Characteristics, and Design

#### Characteristics of the Population:

The trial will involve the recruitment and retention of men and women ( $n=40$ ) with HIV infection who are virally unsuppressed in the United States. Study volunteers must meet general criteria to be eligible for further screening for participation in the study. In most cases, this information will be acquired during a telephone interview prior to a screening/consent remote visit. *The inclusion and exclusion criteria have been carefully*

*selected to enroll the most appropriate study population while also ensuring the generalizability of the findings.* All participants will engage in a 3-month randomized adaptive intervention. The total study duration will be 3 months. A maximum of 25 follow-up interviews will be conducted, with an oversampling of participants in the intervention group.

Potential participants will be recruited online using social media platforms. Persons living with HIV (PLWH) will be included if they meet the following eligibility criteria:

There are limited inclusion criteria in order to support the generalizability of our findings.

**Participants. Inclusion criteria:**

- 1) Able to speak, read, and write in English or Spanish;
- 2) Aged  $\geq 18$  years;
- 3) Willing to provide a valid form of identification for verification;
- 4) Willing to participate in any assigned arm of the intervention;
- 5) Having been diagnosed with HIV  $\geq 6$  months ago;
- 6) Have an HIV-1 RNA level  $>50$  copies/mL, or report either not being virally suppressed in the past 12 months or being virally unsuppressed in the past 12 months;
- 7) Own a smartphone;
- 8) Ability and willingness to provide informed consent for study participation and consent for access to medical records; and
- 9) Live in the United States

**Participants are not eligible if they meet any exclusion criteria:**

- 1) Reside in a nursing home, prison, and/or receiving in-patient psychiatric care at time of enrollment;
- 2) Terminal illness with life expectancy  $<3$  months;
- 3) Planning to move out of the country in the next 3 months.

Our study participants will be recruited nationally.

**Study Procedures, Materials, and Potential Risks**

**Study Procedures and Materials:**

All materials for the proposed study obtained from the participants will be in the form of specimens, EMR information, and data. Principal Investigator (PI), [name], will be responsible for ensuring all information is collected according to the study protocol. Information used to identify potentially eligible participants will be obtained using the NYP-CHP EMR systems. We will also use patient-reported data obtained after consent. Trained and certified professional staff will obtain all data according to detailed study protocols. Data will be collected directly from study participants and their respective EMR and used specifically for research purposes.

The following human subjects-related data elements will be collected for this study with the source(s) of information noted:

- Participant demographic and clinical characteristics including age, sex, gender, race/ethnicity, employment status, and ART adherence (self-report)
- Clinical diagnoses, clinical HIV lab values (viral load), medication history, comorbid health conditions, and primary care visit data (electronic medical records)
- Laboratory measured values of viral load (dried blood spot collection)
- Notes from the CHW encounters with the study participants
- Usage data captured through the WiseApp and the electronic pill bottles (CleverCap)

Our study team is extremely prudent in keeping subject data secure and confidential. All laboratory specimens, evaluation forms, reports, and other records will be identified by a unique coded number to maintain participant confidentiality. The material, records, and data obtained through participation in the study will be specific for research purposes. Existing health records may be used with the permission of the participants. Materials will be obtained by trained staff. Data will be stored using REDCap (Research Electronic Data Capture). All laboratory specimens will be identified *only* by the identification number. The code linking the participant identification number to subject identifying information (name, address, etc.) is maintained through REDCap, and only authorized site personnel have access to the code. Limited individually identifiable private information is collected that is essential for processing participant payments and for analysis purposes.

### Potential Risks:

There is no more than a **minimal risk** associated with any of the proposed study activities. The study activities meet the general definition found in Subpart A (46.102) that the probability and magnitude of harm or discomfort anticipated in the research are not greater in and of themselves than those ordinarily encountered in daily life or during the performance of routine physical or psychological assessments or tests.

The risks of participating in this study are few. Potential risks are those related to dried blood spot collection, discomfort with study interview questions, and potential breaches of confidentiality. It is possible that certain questions on the survey may make participants feel uncomfortable, but participants are free to decline to answer any questions. Additionally, mental health and/or counseling services are available should a participant enter crisis. Participation in research can involve loss of privacy. All study data will be maintained on CUIMC servers that are secure and HIPAA compliant. All signed consent forms, study data, and payment receipts used in this study will be kept in a secured server which only the investigators can access. We will also receive a Federal Certificate of Confidentiality which will protect against attempts by law enforcement or other government agencies to access our data.

